4.3.2 Metastatic Cohorts only

- The safety and tolerability objective will be measured by the incidence of adverse events, serious adverse events, deaths and laboratory abnormalities.
- Pre and post treatment EBV DNA levels will be collected in the subjects with EBV positive gastric cancer (monotherapy only) and nasopharyngeal carcinoma. The change in EBV DNA levels will be used to determine the effect of BMS-936558 (nivolumab).
- Efficacy endpoints in GYN tumor type (monotherapy only) will also be reported in two subgroups, Cervical and Vaginal/Vulvar, when data allows.

4.3.3 Neoadjuvant and Metastatic Cohorts

- **PD-L1 Expression:**

PD-L1 expression missing: Subjects without an available tumor biopsy specimen for PD-L1 evaluation will be considered as PD-L1 expression missing.

For subjects with an available tumor biopsy specimen(s), the following will be considered:

PD-L1 expression is quantified and reported by two methods: tumor proportion score (TPS) and combined positive score (CPS). TPS is defined as the percent of tumor cells membrane staining in a minimum of 100 evaluable tumor cells per validated Dako PD-L1 IHC assay. CPS is evaluated based on the number of viable tumor cells that exhibit PD-L1 membrane staining and associated immune cell (lymphocytes and macrophages) that exhibit PD-L1 membrane and/or cytoplasmic staining. This is referred as quantifiable PD-L1 expression. If the PD-L1 staining could not be quantified, it is further classifies as:

- Indeterminate: PD-L1 staining hampered for reasons attributed to the biology of the tumor tissue sample and not because of improper sample preparation or handling
- Not evaluable: Tumor tissue sample was not optimally collected or prepared (e.g. PD-L1 expression is neither quantifiable nor indeterminate). Not evaluable can be determined from H&E process before the tumor biopsy specimen is sent for PD-L1 evaluation or from the H&E process during PD-L1 evaluation.

If more than one tumor biopsy specimen is available, PD-L1 expression is determined from the most recently collected specimen before first dose date with a quantifiable result. If all specimens for a given subject are either indeterminate or not evaluable, then the PD-L1 expression will be considered indeterminate as long as at least one specimen is indeterminate. Otherwise, PD-L1 expression will be considered not evaluable.

- **Pharmacokinetics:**

The PK objective will be measured from serum concentration. Samples will be collected to characterize pharmacokinetics of nivolumab and to explore exposure-safety and exposure-efficacy relationships.

- **Biomarkers:**

Biomarkers potentially associated with clinical endpoints will be measured by analyzing tumor and blood samples. Biomarker endpoints include, but are not limited to, single-nucleotide polymorphisms (SNPs), proteins in tumor specimens and serum, and immune cell populations.

- **Immunogenicity:**

Serum samples collected will be analyzed by a validated immunogenicity assay. Selected serum samples may be analyzed by an exploratory orthogonal method that measures anti-nivolumab. Potential results generated from any orthogonal method are intended as informational for technology exploration purposes and will not be reported.

In addition, ad hoc serum samples designated for pharmacokinetic or biomarker assessments may also be used for immunogenicity analysis if required (e.g., insufficient volume for complete immunogenicity assessment or to follow up on suspected immunogenicity related AE).

- **EQ-5D:**

Subjects' overall health status will be assessed using the EuroQoL Group's self-reported health status measure (EQ-5D-3L). EQ-5D essentially has 2 components: the EQ-5D descriptive system and the EQ visual analogue scale (EQ-VAS).

The EQ-5D descriptive system comprises the following 5 dimensions: mobility, self-care, usual activities, pain/discomfort and anxiety/depression. Each dimension has 3 levels: no problems, some problems, severe problems. Once the data have been collected and a database created, a scoring function can be used to assign a value (i.e., EQ-5D index score) to self-reported health states from a set of population-based preference weights.

The EQ VAS records the subject's self-rated health state on a 100-point vertical, visual analogue scale (0 = worst imaginable health state; 100 = best imaginable health state).

- **EORTC-QLQ-C30:**

Health-related quality of life (HRQoL) will be assessed using the European Organization for Research and Treatment of Cancer (EORTC) QLQ-C30 questionnaire Version 3. It is a 30-item instrument that has gained wide acceptance in oncology clinical studies. The EORTC QLQ-C30 is composed of multi-item and single scales. These include five functional scales (physical, role, emotional, social, and cognitive), three symptom (fatigue, nausea and vomiting and pain) and a global health status/QOL scale and six single items (dyspnea, insomnia, appetite loss, constipation, diarrhea and financial difficulties). All scales and single items meet the standards for reliability. The reliability and validity of the questionnaire is highly consistent across different language-cultural groups². Except for the overall health status and global quality of life items, responses for all items are 4-point categorical scales ranging from 1 (Not at all) to 4 (Very much). The overall health status/quality of life responses are 7-point Likert scales.

Data will be scored according to the algorithm described in the EORTC QLQ-C30 scoring manual, as follows:

Functional scales:

- Physical functioning: $(1 - ((Q1+Q2+Q3+Q4+Q5)/5-1)/3) * 100$
- Role functioning: $(1 - ((Q6+Q7)/2-1)/3) * 100$
- Emotional functioning: $(1 - ((Q21+Q22+Q23+Q24)/4-1)/3) * 100$
- Cognitive functioning: $(1 - ((Q20+Q25)/2-1)/3) * 100$
- Social functioning: $(1 - ((Q26+Q27)/2-1)/3) * 100$

Global health status:

- Global health status/QoL: $((Q29+Q30)/2-1)/6 * 100$

Symptom scales/items:

- Fatigue: $((Q10+Q12+Q18)/3-1)/3 * 100$
- Nausea and vomiting: $((Q14+Q15)/2-1)/3 * 100$
- Pain: $((Q9+Q19)/2-1)/3 * 100$
- Dyspnea: $(Q8-1)/3 * 100$
- Insomnia: $(Q11-1)/3 * 100$
- Appetite loss: $(Q13-1)/3 * 100$
- Constipation: $(Q16-1)/3 * 100$
- Diarrhea: $(Q17-1)/3 * 100$
- Financial difficulties: $(Q28-1)/3 * 100$

Missing values will be imputed for missing items by “assuming that the missing items have values equal to the average of those items which are present” for any scale in which at least half the items are completed. A scale in which less than half of the items are completed will be treated as missing. This is the method proposed in the scoring manual. A questionnaire will be considered as received if at least one of the 15 scales is non-missing (after imputation).

All questionnaires completed at baseline and on-study will be assigned to a time-point according to the windowing criteria in Table 4.3-3 and included in the analysis. In case a subject has two on-study assessments within the same window, the assessment closest to the time-point will be used. And, in the case of two assessments at a similar distance to the time-point, the latest one will be chosen. In the event where the subject has no assessment at all in a specific window, the observation will be treated as missing for that time-point.

Table 4.3-3: Time Windows for EORTC-QLQ-C30 and EQ-5D Assessments

Nominal Time-Point	Time Window
Nivolumab Monotherapy Metastatic Cohorts	

Table 4.3-3: Time Windows for EORTC-QLQ-C30 and EQ-5D Assessments

Nominal Time-Point	Time Window
Baseline	Prior to first dose on Day 1
Week 9	Day 2 thru Day 85, inclusive
Every 8 Weeks up to week 25	Nominal Day (+28 days/-27 days, inclusive)
Week 33	Nominal Day 225 (+42 days/-27 days, inclusive)
Every 12 weeks thereafter	Nominal Day (+42 days/-41 days, inclusive)
Follow-up 1	Any data associated with Follow-up X01 visit
Follow-up 2	Any data associated with Follow-up X02 visit
Survival Follow-up Visits (applies to EQ-5D only)	
Survival Follow-up Visit 1	Any data associated with Survival Follow-up Visit 1
Survival Follow-up Visit 2	Any data associated with Survival Follow-up Visit 2
...	...
Nivolumab Monotherapy Neoadjuvant Cohorts	
Baseline	Prior to first dose on Day 1
Week 3	Day 2 thru Day 28 or the day before surgery/biopsy date, whichever is earlier, inclusive.
SOC Follow-up 1	Any data associated with Follow-up E01 visit
SOC Follow-up 2	Any data associated with Follow-up E02 visit
Post SOC Week 1	Post SOC Day 1 (prior to first dose of post SOC Nivo)
Post SOC Week 9	Post SOC Day 2 thru Post SOC Day 85, inclusive
Post SOC Week 17	Post SOC Day 86 thru Post SOC Day 141, inclusive
Post SOC Week 25	Post SOC Day 142 thru Post SOC Day 197, inclusive
Post SOC Week 33	Post SOC Day 198 thru Post SOC Day 267, inclusive
Every 12 weeks thereafter	Nominal Post SOC Day (+42 days/-41 days, inclusive)
Follow-up 1	Any data associated with Follow-up X01 visit
Follow-up 2	Any data associated with Follow-up X02 visit
Survival Follow-up Visits (applies to EQ-5D only)	
Survival Follow-up Visit 1	Any data associated with Survival Follow-up Visit 1
Survival Follow-up Visit 2	Any data associated with Survival Follow-up Visit 2
...	...
Nivolumab combination therapy A, C, D treatment group	
Same as Nivolumab Monotherapy Metastatic Cohorts	

Table 4.3-3: Time Windows for EORTC-QLQ-C30 and EQ-5D Assessments

Nominal Time-Point	Time Window
Nivolumab combination therapy B treatment group	
Baseline	Prior to first dose on Day 1
Week 10	Day 2 thru Day 99, inclusive
Week 19	
Week 27	Day 100 thru Day 155, inclusive
Week 35	Day 156 thru Day 211, inclusive
Week 47	Day 212 thru Day 267, inclusive
Every 12 weeks thereafter	Nominal Day 323 (+42 days/-55 days, inclusive) Nominal Day (+42 days/-41 days, inclusive)
Follow-up 1	Any data associated with Follow-up X01 visit
Follow-up 2	Any data associated with Follow-up X02 visit
Survival Follow-up Visits (applies to EQ-5D only)	
Survival Follow-up Visit 1	Any data associated with Survival Follow-up Visit 1
Survival Follow-up Visit 2	Any data associated with Survival Follow-up Visit 2
...	...

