| Procedure | Combo A During Treatment Nivo 3mg q2w + Ipi 1 mg/kg q6w | Combo B During Treatment Nivo 1 mg/kg + Ipi 3 mg/kg q3w x 4, followed by Nivo 240 mg q2w | Combo C During Treatment Nivo 240 mg + BMS-986016 80 mg q2w | Combo D During Treatment Daratumumab q1 week/q2weeks/q4 weeks + Nivo 240 mg q2 weeks/ 480 mg every 4 wks. | Notes See note sections below for dosing windows |
|--------------------------------------|--|---|---|--|--|
| Outcomes Research Assessments | | | | | |
| EORTC QLQ-C30 (Cohorts A, C, and D) | X | | X | X | Assessments to be collected at Day 1 Week 1 every 4 cycles for the first 17 cycles: Day 1 (prior to dosing) of Cycles 1, 5, 9, 13, 17; Then every 6 cycles thereafter: Day 1 (prior to dosing) of Cycles 23, 29, 35+. |
| EORTC QLQ-C30 (Cohort B) | | X | | | Assessments to be collected prior to dosing at Cycle 1 Day 1 and Cycle 4 Day 1, and then every 4 cycles for 16 cycles: Day 1 (prior to dosing) Cycles 1, 4, 8, 12, 16; Then every 6 cycles thereafter: Day 1 (prior to dosing) Cycles 22, 28, 34+ |
| EQ-5D (Cohort A, C, and D) | X | | X | X | Assessments to be collected at Day 1 Week 1 every 4 cycles for the first 17 cycles: Day 1 (prior to dosing) of Cycles 1, 5, 9, 13, 17; every 6 cycles thereafter: Day 1 (prior to dosing) of Cycles 23, 29, 35+. |

Table 5.1-3: On-Treatment Assessments Metastatic Combination Therapy Cohorts (CA209358)

| Procedure | Combo A During Treatment Nivo 3mg q2w + Ipi 1 mg/kg q6w | Combo B During Treatment Nivo 1 mg/kg + Ipi 3 mg/kg q3w x 4, followed by Nivo 240 mg q2w | Combo C During Treatment Nivo 240 mg + BMS-986016 80 mg q2w | Combo D During Treatment Daratumumab q1 week/q2weeks/q4 weeks + Nivo 240 mg q2 weeks/ 480 mg every 4 wks. | Notes See note sections below for dosing windows |
|------------------|--|---|---|--|---|
| EQ-5D (Cohort B) | | X | | | 
Assessments to be collected prior to dosing at Cycle 1 Day 1 and Cycle 4 Day 1, and then every 4 cycles for 16 cycles:
 
Day 1 (prior to dosing) Cycles 1, 4, 8, 12, 16;
 
Then every 6 cycles thereafter:
 
Day 1 (prior to dosing) Cycles 22, 28, 34+
 |

Table 5.1-3: On-Treatment Assessments Metastatic Combination Therapy Cohorts (CA209358)

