^d Cycle 4 pertains to the nivolumab every 4 week (q4w) regimen; Cycle 7 pertains to the nivolumab every 2 week (q2w) regimen.

Table 5.5-7: Pharmacokinetic and Immunogenicity Sampling Schedule for Nivolumab (Nivolumab and Daratumumab Combination - Combo D)

| Study Day (1 Cycle = 1 week from Weeks 1-8 1 Cycle = 2 weeks from Weeks 9-24 1 Cycle = 4 weeks from Week 25) | Event (Relative to Start of Infusion/Event) | Time (Relative to Start of Nivolumab Infusion) Hour:Min | PK Blood Sample for Nivolumab | Immunogenicity Sample for Nivolumab |
|---|--|---|-------------------------------|-------------------------------------|
| Cycle 3 Day 1 (Week 3 Day 1) ^a | Predose ^b | 00:00 | X | X |
| Cycle 9 Day 1(Week 9 Day 1) | Predose ^b | 00:00 | X | X |
| Cycle 11 Day 1(Week 13 Day 1) | Predose ^b | 00:00 | X | X |
| Cycle 17 day 1 (Week 25 Day 1) ^c | Predose ^b | 00:00 | X | X |
| Day 1 of every 4th cycle (every 16 weeks) until discontinuation of study treatment or up to 2 years of treatment | Predose ^b | 00:00 | X | X |

^a Nivolumab will start at Week 3.

^b Pre-dose samples should be taken prior to the start of both nivolumab and daratumumab infusion. If the infusion is delayed and a pre-dose sample is already collected, there is no need to collect an additional pre-dose sample

^c Starting from Week 25, nivolumab will be given 480 mg Q4W

Table 5.5-8: Pharmacokinetic and Immunogenicity Sampling Schedule for Daratumumab (Nivolumab and Daratumumab Combination - Combo D)

| Study Day | Event (Relative to Start of Daratumumab Infusion/Event) ^a | Time (Relative to Start of Daratumumab Infusion) Hour:Min | PK Blood Sample for Daratumumab | Immunogenicity Assessment for Daratumumab (taken from Dara PK sample) ^b |
|---------------|---|---|---------------------------------|--|
| Week 1 Day 1 | Predose ^a | 00:00 | X | X |
| Week 1 Day 1 | Postdose | EOI | X | |
| Week 5 Day 1 | Predose | 00:00 | X | X |
| Week 5 Day 1 | Postdose | EOI | X | |
| Week 9 Day 1 | Predose ^a | 00:00 | X | X |
| Week 13 Day 1 | Predose ^a | 00:00 | X | X |

Table 5.5-8: Pharmacokinetic and Immunogenicity Sampling Schedule for Daratumumab (Nivolumab and Daratumumab Combination - Combo D)

| Study Day | Event (Relative to Start of Daratumumab Infusion/Event) ^a | Time (Relative to Start of Daratumumab Infusion) Hour:Min | PK Blood Sample for Daratumumab | Immunogenicity Assessment for Daratumumab (taken from Dara PK sample) ^b |

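### The SAP applies 2-week-cycle questionnaire windows to Combo D, whose cycles run 1, 2 and then 4 weeks, so several windows do not match the planned visits

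*SAP*

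**What the plan says.** SAP Section 4.3.3 assigns every completed questionnaire to a time point through Table 4.3-3. The row headed "Nivolumab combination therapy A, C, D treatment group" contains only "Same as Nivolumab Monotherapy Metastatic Cohorts". The monotherapy windows it points to are:

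- Week 9: "Day 2 thru Day 85, inclusive"
- Weeks 17 and 25: "Nominal Day (+28 days/-27 days, inclusive"
- Week 33: "Nominal Day 225 (+42 days/-27 days, inclusive"
- every 12 weeks after that: "Nominal Day (+42 days/-41 days, inclusive"

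When two forms fall in one window, the SAP uses the one nearer the nominal day. A window with no form counts as missing for that time point.

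Protocol Table 5.1-3 schedules both questionnaires for Cohorts A, C and D at "Day 1 (prior to dosing) of Cycles 1, 5, 9, 13, 17", and then at Cycles 23, 29 and 35 onward. The only explicit definition of a Combo D cycle is in protocol Table 5.5-7: "1 Cycle = 1 week from Weeks 1-8 1 Cycle = 2 weeks from Weeks 9-24 1 Cycle = 4 weeks from Week 25".

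**The concern.** A window table works only if its nominal days match the days on which forms are due. The monotherapy windows match a 2-week cycle. Combo D changes cycle length twice, so the same cycle numbers fall on different calendar days. Where the two disagree, a completed form can be displaced by a neighbour, a later form can carry the wrong week label, and a time point can show almost no data because no visit was planned there. SAP Sections 7.10.1 and 7.10.2 report change from baseline at each time point by tumor type, and Combo D is its own group (MC-7d in SAP Section 6.3.1). The mismatch would therefore be fully visible in that arm's tables, and could be read as drop-out.

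**Working it through.** **Inputs.** Windows: SAP Table 4.3-3. Questionnaire cycles: protocol Tables 5.1-2 (monotherapy) and 5.1-3 (Combo D). Monotherapy cycle of 14 days: protocol Section 4.5. Combo D cycle lengths: protocol Table 5.5-7.

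**Reproducing the plan's own figure.** Nominal day = 7 × (week − 1) + 1. For monotherapy, the week of cycle c is 1 + 2(c − 1). Cycle 17 gives Week 33, and 7 × 32 + 1 = Day 225, the SAP's stated day. Cycles 5, 9, 13, 17, 23, 29 and 35 fall on Days 57, 113, 169, 225, 309, 393 and 477, each exactly on a nominal day. The windows fit monotherapy.

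**Combo D days under Table 5.5-7.**

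- c ≤ 9: day = 7(c − 1) + 1
- 9 < c ≤ 17: day = 57 + 14(c − 9)
- c > 17: day = 169 + 28(c − 17)

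As a check, Cycles 3, 9, 11 and 17 give Days 15, 57, 85 and 169, which are Weeks 3, 9, 13 and 25, as Table 5.5-7 states.

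**Questionnaire visits.** Cycle 5: 7 × 4 + 1 = 29. Cycle 9: 57. Cycle 13: 57 + 56 = 113. Cycle 17: 57 + 112 = 169. Cycle 23: 169 + 168 = 337. Cycle 29: 169 + 336 = 505. Cycle 35: 169 + 504 = 673. These are Weeks 5, 9, 17, 25, 49, 73 and 97.

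**Placing the visits in the SAP windows.**

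| SAP time point | Window (days) | Combo D visits due | Distance from nominal |
|---|---|---|---|
| Week 9 | 2–85 | Days 29 and 57 | −28 and 0 |
| Week 17 | 86–141 | Day 113 | 0 |
| Week 25 | 142–197 | Day 169 | 0 |
| Week 33 | 198–267 | none | – |
| Week 45 | 268–351 | Day 337 | +28 |
| Week 57 | 352–435 | none | – |
| Week 69 | 436–519 | Day 505 | +28 |
| Week 81 | 520–603 | none | – |
| Week 93 | 604–687 | Day 673 | +28 |

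In the Week 9 window, Day 57 is 0 days from nominal and Day 29 is 28 days away, so Day 57 is used. If the Day 57 form is absent, the Day 29 form is reported as Week 9.

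**Late dosing.** From Week 25, protocol Section 4.5 allows a daratumumab delay of up to 14 days and Table 5.1-3 allows up to 21.

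- Cycle 17 moves to Day 169 + 14 = 183 or 169 + 21 = 190. Both are at or before Day 197, so Week 33 stays empty either way.
- With 14 days, the later visits move to Days 351, 519 and 687, the last days of their windows. Nothing changes.
- With 21 days, they move to Days 358, 526 and 694. Weeks 57, 81 and 105 then fill, and Weeks 45, 69 and 93 become empty.

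Longer toxicity holds under protocol Section 4.7.3 could move an individual subject further and are not part of this check.

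**The case against.** The strongest objection is to the premise. The 1/2/4-week definition stands only in a pharmacokinetic sampling table. Table 5.1-3, which schedules the questionnaires, does not define a Combo D cycle, and its laboratory note for Cohorts A, C and D equates 6 weeks with 3 nivolumab cycles. On a constant 2-week count the copied windows would fit exactly. Part of this stands: no passage says outright which count governs Combo D questionnaires. But the laboratory note is shared by three cohorts and cannot describe Combo D from Week 25, when protocol Table 4.5-1 gives nivolumab every 4 weeks. SAP Table 7.4.1-1 uses 1-, 2- and 4-week cycle durations for daratumumab, and 2 then 4 weeks for nivolumab. Counting nivolumab doses from Week 3 puts Cycles 5, 9, 13, 17, 23 and 29 on Days 71, 127, 197, 309, 477 and 645. Weeks 33, 57 and 81 are still empty on schedule. Only the Week 5 collision depends on Table 5.5-7.

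The second objection is to the harm, and most of it stands. A reader might infer that every subject loses a form, that data are thrown away, or that the reported values are wrong. The documents support none of these. Day 29 is displaced only when a Day 57 form exists. The listings in SAP Sections 7.10.1 and 7.10.2 keep all forms. No score or change value is altered. A visit 28 days past nominal is inside the SAP's own +42-day limit. Completion rates and problem-level percentages use subjects assessed at the time point, so an empty window does not depress them.

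Third, the arm has ended. Enrollment closed on 26-May-2018 and the combination was then stopped (protocol Section 3.1.1). Even a subject dosed on 28-Oct-2016, the date of the amendment that added the arm, would have reached only Day 629 (365 + 263 days elapsed, plus 1) by Revised Protocol 06 on 18-Jul-2018, short of Day 673. Some subjects could continue on nivolumab alone (Section 1.1.12), and no document says which cycle count would then apply.

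**Conclusion.** The point holds as a minor one. On the planned schedule, the windows assigned to Combo D leave the Week 5 form out of the summaries for subjects with both early forms, leave three time points without a scheduled visit, and label three later visits 28 days early. This rests on the Table 5.5-7 cycle count and on dosing to schedule.

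It would go too far to say that Weeks 57 and 81 are empty whatever happens, because the 21-day allowance can fill them. Week 33 stays empty under either stated dosing window on the Table 5.5-7 count.

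The consequence is limited to descriptive, exploratory summaries in one terminated arm of at most about 40 subjects, few of whom would reach the late windows. No primary, secondary or safety result is touched. The early collision does not depend on long treatment and so is the part most likely to matter.

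**What to change.** 1. State in the SAP that the Table 5.5-7 cycle count governs Combo D questionnaires. This has to come first. If a constant 2-week count turned out to apply, the rows below would put Days 169 and 225 in one window and Days 309 and 393 in another, and leave Week 5 empty.
2. Once confirmed, give Combo D its own rows in Table 4.3-3, as Combo B has, centred on Weeks 5, 9, 17, 25, 49, 73 and 97. Boundaries midway between visits give Days 2–43, 44–85, 86–141, 142–253, 254–421, 422–589 and, using the same 84-day half-interval, 590–757.
3. Limit the shared row to Combo A and to Combo C subjects dosed every 2 weeks.
4. Reconcile the 14-day and 21-day Combo D dosing windows in protocol Section 4.5 and Table 5.1-3.

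The cost is one SAP table edit, one clarifying sentence and a programming parameter. No new data are needed.

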2.2 Treatment Assignment

After the subject's informed consent has been obtained and eligibility is established, the subject will be enrolled and a number will be assigned through an interactive voice response system (IVRS). If the tumor group for which the subjects would be assigned to has not yet met the expected number of subjects for the study, the subject will be assigned a treatment vial number and will receive study treatment.

Neoadjuvant Cohort:

- Nivolumab administered intravenously (IV) over 30 minutes at 240 mg for 2 doses, on Day 1 and Day 15 (before surgery).

Metastatic Monotherapy Cohort:

- Nivolumab administered IV over 30 minutes at 240 mg every 2 weeks for a maximum of 24 months or until disease progression, unacceptable toxicity, or withdrawal of consent, whichever comes first.

Metastatic Combination Cohorts (Combinations A, B, C, and D):

- Combo Arm A: Nivolumab 3 mg/kg IV over 30 minutes every 2 weeks plus Ipilimumab 1 mg/kg IV over 30 minutes every 6 weeks for a maximum of 24 months or until disease progression, unacceptable toxicity, or withdrawal of consent, whichever comes first.
- Combo Arm B: Nivolumab 1 mg/kg IV over 30 minutes plus Ipilimumab 3 mg/kg IV over 30 minutes every 3 weeks for 4 doses followed by Nivolumab 240 mg IV over 30 minutes every 2 weeks for a maximum of 24 months or until disease progression, unacceptable toxicity, or withdrawal of consent, whichever comes first.
- Combo Arm C: Nivolumab 480 mg IV over 30 minutes plus BMS-986016 160 mg IV over 60 minutes administered every 4 weeks for a maximum of 24 month, or until disease progression, unacceptable toxicity, or withdrawal of consent, whichever comes first. Subjects enrolled in Combo C prior to Revised Protocol 05 and on treatment with BMS-986016 80 mg + Nivolumab 240 mg q2W will remain on this dose regimen for the duration of their time on treatment.
- Combo Arm D: Daratumumab 16 mg/kg IV administered weekly for the first 8 weeks. Starting at Week 3, nivolumab 240 mg IV over 30 minutes will be administered every 2 weeks. Nivolumab will be administered before the daratumumab infusion on study days when both study drugs are administered on the same day. Daratumumab 16 mg/kg will be administered every 2 weeks from Weeks 9-24. Starting at Week 25, nivolumab 480 mg IV

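### Combo B questionnaire windows part Week 35 from Week 47 at Day 267/268, not at the Day 281 midpoint, so a Cycle 16 form 29 to 41 days late is labelled Week 47

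*SAP*

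**What the plan says.** Protocol Table 5.1-3 ties the Combo B questionnaires to dosing cycles, first "Day 1 (prior to dosing) Cycles 1, 4, 8, 12, 16" and then "Day 1 (prior to dosing) Cycles 22, 28, 34" onward. A delayed dose therefore delays the form. SAP Section 2.2 gives the dosing rhythm that fixes the cycle days: "every 3 weeks for 4 doses followed by Nivolumab 240 mg IV over 30 minutes every 2 weeks".

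SAP Section 4.3.3, Table 4.3-3, assigns each form to a time point by study day. For combination B, the window that contains the Week 35 day is "Day 212 thru Day 267, inclusive", and Week 47 is "Nominal Day 323 (+42 days/-55 days, inclusive"). Later visits are 12-weekly with +42/-41 days. For metastatic monotherapy, the last 8-weekly visit (Week 33) is "Nominal Day 225 (+42 days/-27 days, inclusive"), and the 12-weekly visits after it have +42/-41.

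The same section settles duplicates: "In case a subject has two on-study assessments within the same window, the assessment closest to the time-point will be used". A window with no form is treated as missing.

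**The concern.** Both schedules change from 8-weekly to 12-weekly forms, and at that change the gap between nominal days grows from 56 to 84 days. The monotherapy rows widen the late side of the last 8-weekly window to match. The Combo B rows keep the 8-weekly late edge of +28 for Week 35 and give the rest of the gap to Week 47. The result is a -55/+42 window that reaches back past the midpoint.

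At stake are the by-visit descriptive summaries in SAP Sections 7.10.1 and 7.10.2: change from baseline, the percentage with clinically meaningful deterioration, completion rates and the EQ-5D results at Weeks 35 and 47. A late Cycle 16 form can be lost, or shown under a visit 12 weeks after the one it was collected for.

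**Working it through.** **Inputs.** Cycle lengths from SAP Section 2.2, questionnaire cycles from Protocol Table 5.1-3, windows from SAP Table 4.3-3. In the text read for this review the Combo B labels and windows sit slightly out of line, so each window was matched to the nominal day it contains. Only Days 212 to 267 contain Day 239.

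**Nominal days.** Cycle 5 starts on Day 1 + 4 x 21 = 85, and later cycles follow every 14 days. Week = (day - 1)/7 + 1.

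| Cycle | Day | Week | SAP window | Offsets | Midpoint to next visit |
|---|---|---|---|---|---|
| 4 | 64 | 10 | 2-99 | | 95.5 |
| 8 | 127 | 19 | 100-155 | -27/+28 | 155 |
| 12 | 183 | 27 | 156-211 | -27/+28 | 211 |
| 16 | 239 | 35 | 212-267 | -27/+28 | **281** |
| 22 | 323 | 47 | 268-365 | -55/+42 | 365 |

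The SAP's own figures reproduce: Cycle 22 is Day 323, 323 - 55 = 268 and 323 + 42 = 365. The windows neither gap nor overlap.

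**The cut.** (239 + 323)/2 = 281. The SAP cuts after Day 267, 14 days earlier. Days 268 to 280 (13 days) are 29 to 41 days after Day 239 and 43 to 55 days before Day 323. Day 281 is equidistant.

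**Monotherapy comparison.** Week 33 is Day 225 and the next visit is Day 225 + 84 = 309, so the midpoint is 267. The SAP has 225 + 42 = 267 and 309 - 41 = 268, which is the midpoint cut.

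**When both forms share Week 47.** A Cycle 22 form follows Cycle 16 by at least 6 x 12 = 72 days (12-day minimum spacing, Protocol Section 4.5), so it falls on Day 340 or later. If it is inside the window it is at most 42 days from Day 323, while the Cycle 16 form is 43 to 55 days away. Cycle 22 always wins. If the delay is carried forward unchanged, Cycle 22 falls on Days 352 to 364. It leaves the window only with a further slip of 14 days (Cycle 16 was 29 days late) down to 2 days (41 days late).

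**Reach.** The 6-week limit between doses (Protocol Section 4.5) means one 2-weekly dose can be at most 42 - 14 = 28 days late. Then 239 + 28 = 267, which is still Week 35. A slip of 29 to 41 days needs more than one delay or an exception under Protocol Section 4.7.6.

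**Cases.** In A and B, Cycle 12 is 14 days late (Day 197). One interval of 35 instead of 14 days before Cycle 16 then gives 197 + 56 + 21 = Day 274, and Cycle 22 falls on Day 274 + 84 = 358. In C and D the subject is already 35 days late at Cycle 12 (Day 218).

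| Case | Forms on days | SAP windows | Midpoint cut |
|---|---|---|---|
| A | 197, 274, 358 | Week 35 missing; Week 47 = Cycle 22 (35 v 49 days); Cycle 16 dropped | Week 35 = Cycle 16; Week 47 = Cycle 22 |
| B | 197, 274, no Cycle 22 | Week 35 missing; Week 47 = Cycle 16 | Week 35 = Cycle 16; Week 47 missing |
| C | 218, 274, 358 | Week 35 = Cycle 12; Cycle 16 dropped; Week 47 = Cycle 22 | Same as SAP (Cycle 12 is 21 days from Day 239, Cycle 16 is 35) |
| D | 218, 274, no Cycle 22 | Week 35 = Cycle 12; Week 47 = Cycle 16 | Week 35 = Cycle 12; Week 47 missing |

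A slip of 29 to 41 days already present at Cycle 12 puts that form on Days 212 to 224, 15 to 27 days from Day 239. It always beats Cycle 16 for Week 35.

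**The case against.** The SAP states no midpoint rule, its subtractions are right, and Combo B Weeks 19, 27 and 35 all use -27/+28. On that view Day 267 continues a pattern and is only a convention. This stands as far as it goes: one cannot show that the boundary was copied from monotherapy, where Days 267/268 also occur. But +28 is half of a 56-day gap, and the gap after Week 35 is 84 days. The Combo B cuts at Days 155, 211 and 365 are midpoints, as are the monotherapy cuts, and no reason is given for -55. The Week 10/19 cut is also off its midpoint (99 against 95.5), by about 4 days.

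Four stronger readings are tempting, and the documents do not support them:

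- *The late form is always discarded.* It is discarded only if a Cycle 22 form falls in Days 268 to 365. Otherwise it is kept under the wrong label.
- *Week 35 is always left missing.* Not if the slip was already 29 to 41 days at Cycle 12 (cases C and D).
- *A monotherapy subject with the same slip keeps the form.* With a constant 35-day slip, Cycle 13 falls on Day 204 and Cycle 17 on Day 260, both in Week 33. Cycle 13 is 21 days from Day 225 and Cycle 17 is 35, so Cycle 17 is dropped there too.
- *A known share of forms is lost and Week 35 quality of life looks better as a result.* Neither document gives the distribution of delays at Cycle 16 or any link between delay and scores. The planned 110 Combo B cervical subjects (SAP Table 5-4) are not the number still treated at Cycle 16.

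**Conclusion.** The inconsistency is real and can change reported results within the protocol's dosing rules, as case A shows. Its size is 13 days of an 84-day gap, affecting Cycle 16 forms that are 29 to 41 days late. For those forms the Week 47 label is wrong by the midpoint logic used in the rest of the transition. Whether the form is lost depends on Cycle 22, and whether Week 35 is empty depends on Cycle 12.

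This rests on reading Days 212 to 267 as the Week 35 window and on the nominal cycle days above. The frequency and any direction of bias are unknown. The questionnaires are exploratory and summarised descriptively, by-subject listings are planned, and no primary or secondary analysis is affected. It is a minor correction worth making.

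**What to change.** In Table 4.3-3, combination B, set Week 35 to Day 212 through Day 281 (nominal Day 239, +42/-27) and Week 47 to nominal Day 323 with +42/-41 (Day 282 through Day 365). This matches the monotherapy rows, including giving the equidistant day to the earlier visit. Review the Week 10/19 cut in the same edit.

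The cost is two numbers in one SAP table and the matching windowing code, with no change to data collection. The edit recovers Week 35 in cases like A and B. In cases like D it only stops a Cycle 16 form being reported as Week 47, and in cases like C it changes nothing.
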